### **8.2.3. Low Luminance Best-Corrected Visual Acuity (LL-BCVA)**

The change from baseline in LL-BCVA score over time to Month 12 will be analysed in the same way as the BCVA endpoint (Section 8.2.1) for the MITT population.

The analysis model table will be presented. The treatment comparisons (AM vs Sham, AEOM vs Sham and AM vs AEOM) at Months 6 and 12 will also be presented with the estimate, standard error and 95% CI. If the treatment effect is significant at the 10% level then the treatment means will be compared using the least significant difference (LSD) method and the p-value presented.

The change from baseline in LL-BCVA score will be summarized by treatment group and visit for the MITT population using the observe data. Summaries will present the descriptive statistics for baseline, absolute values and change from baseline data.

The estimated mean change from baseline in LL-BCVA score with ± SE of mean change, will be plotted over time by treatment group. The plot will be repeated for the observed mean change from baseline in BCVA score ± SE of mean change.

The categorical changes (improvements of ≥5 to <10, ≥10 to <15 and ≥15, minimal change, worsening of ≥5 to <10, ≥10 to <15 and ≥15, and missing changes) will be summarized by treatment group and visit for the MITT population.

The Snellen equivalent categorical response will be summarized by treatment group and visit for

## Statistical Analysis Plan

---

the MITT population. The observed logMAR changes from baseline will also be summarized by treatment group and visit for the MITT population. The listing of LL-BCVA data will also include the logMAR values.

The relationship between GA lesion size change from baseline as recorded by FAF and changes from baseline in LL-BCVA will also be investigated. A scatter plot of changes from baseline at Month 12 in GA lesion size as measured by FAF versus changes from baseline at Month 12 in LL-BCVA score will be presented. Treatment groups will be identified on the plot. The Pearson correlation coefficient for each treatment group will also be presented. Similar summary and figures will be provided for relationship at Month 18. To assess whether there is a delay in LL-BCVA decline compared to GA growth, the scatter plot of the changes from baseline for GA lesion at Month 6 vs LL-BCVA at Month 12, and GA lesion at Month 12 vs LL-BCVA at Month 18 will be provided.

### **8.2.4. Low Luminance Visual Acuity (LL-VA) Deficit**

The change from baseline in LL-VA deficit over time to Month 12 will be analysed in the same way as the BCVA endpoint (Section 8.2.1) for the MITT population.

The analysis model table will be presented. The treatment comparisons (AM vs Sham, AEOM vs Sham and AM vs AEOM) at Months 6 and 12 will also be presented with the estimate, standard error and 95% CI. If the treatment effect is significant at the 10% level then the treatment means will be compared using the least significant difference (LSD) method and the p-value presented.

The change from baseline in LL-VA Deficit will be summarized by treatment group and visit for the MITT population using the observe data. Summaries will present the descriptive statistics for baseline, absolute values and change from baseline data.

The estimated mean change from baseline in LL-VA deficit with  $\pm$  SE of mean change, will be plotted over time by treatment group. The plot will be repeated for the observed mean change from baseline in LL-VA deficit  $\pm$  SE of mean change.

### **8.2.5. Foveal Encroachment (Distance of GA Lesion from Fovea)**

The change from baseline in distance of GA lesion from fovea over time to Month 12 will be analysed in the same way as the primary endpoint (Section 8.1) for the MITT population.

The analysis model table will be presented. The treatment comparisons (AM vs Sham, AEOM vs Sham and AM vs AEOM) at Months 2, 6 and 12 will also be presented with the estimate, standard error and 95% CI. If the treatment effect is significant at the 10% level then the treatment means will be compared using the least significant difference (LSD) method and the p-value presented.

The change from baseline in foveal encroachment will be summarized by treatment group and visit for the MITT population using the observe data. Summaries will present the descriptive statistics

## Statistical Analysis Plan

---

for baseline, absolute values and change from baseline data.

The observed mean change from baseline in distance of GA lesion from fovea with  $\pm$  SE of mean change, will be plotted over time by treatment group.

### **8.2.6. Drusen Size**

Study eye drusen size (none, small, intermediate or large) and number of intermediate/large drusen collected at baseline and end of study will be summarized by treatment group for the MITT population with a shift table relative to baseline. Marginal totals will be included and missing data will also be summarized. The end of study visit will be summarized including and excluding subjects who discontinued treatment early.

### **8.2.7. GA Lesion Size Measured by SD-OCT**

The change from baseline in square root area for GA lesion over time to Month 12 as measured by SD-OCT will be analysed for the subset of subjects who have data, in the same way as the primary endpoint for the MITT population.

The analysis model table will be presented. The treatment comparisons (AM vs Sham, AEOM vs Sham and AM vs AEOM) at Months 2, 6 and 12 will also be presented with the estimate, standard error and 95% CI. If the treatment effect is significant at the 10% level then the treatment means will be compared using the least significant difference (LSD) method and the p-value presented.

The change from baseline in square root area for GA lesion will be summarized by treatment group and visit for the MITT population using the observe data. Summaries will present the descriptive statistics for baseline, absolute values and change from baseline data.

### **8.2.8. Genetic Polymorphisms**

Genetic marker analysis will be performed by The Institute of Human Genetics at the University of Regensburg. The relationship of the primary endpoint and each gene will be investigated. The analysis will be documented in a separate report and included in the CSR as an appendix.

### **8.2.9. Other Ophthalmology Data**

All other ophthalmology data collected but not discussed in other sections of the SAP will be listed by treatment group. The ophthalmology assessments performed in this study include the following:

- Fundus Autofluorescence Photographs (FAF)
- SD-OCT
- Digital Color Fundus Photographs (DCFP)
- Fundus Fluorescein Angiograms (FFA)

## Statistical Analysis Plan

---

- Infrared Reflectance (IR)
- BCVA and LL-BCVA

### 9. ANALYSIS OF PHARMACOKINETICS

#### 9.1. CONCENTRATION DATA

The APL-2 trough concentrations will be evaluated using the PK population. APL-2 trough concentrations will be summarized by treatment group at each protocol specified time point using descriptive statistics including the interquartile range. The number of subjects with a BLQ value will also be tabulated.

Linear and log-linear individual trough concentration profile plots against time will be produced for each APL-2 treatment group. The actual sampling time will be used on the x-axis.

Linear and log-linear median trough concentration profile plots against time will be produced by treatment group. The nominal sampling time will be used on the x-axis.

A listing of all trough concentration data will be presented by treatment group.

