4.1.3.1 Pharmacokinetics

Pharmacokinetic parameters after IVT injections have been assessed in cynomolgus monkeys receiving a single injection of 10 mg of APL-2 in each eye. Vitreous humor APL-2 concentrations ranged from 706 to 3060 μ g/mL on Day 2 (first sampling time point). There was an exponential decline in APL-2 concentrations over time and IVT concentrations ranging from below-quantification-level (BQL) to 11.6 μ g/mL were reported on Day 28. From these data, an IVT half-life ($t_{1/2}$) of approximately 3.2 days was calculated. Serum concentrations peaked between Days 7 and 10, and ranged from 13.4 to 62.0 μ g/mL at their maximum. There was an exponential decline in APL-2 concentrations afterwards and concentration ranging from 2.43 to 17.3 μ g/mL where measured on Day 28. The apparent APL-2 serum half-life ($t_{1/2}$) after IVT injection was 10.4 days.

Intravitreal injections every 4 weeks in monkeys do not seem to cause significant drug accumulation in vitreous humor or serum based on available PK data from the 9-month ocular study. Mean intravitreal APL-2 concentrations increased slightly between the first and second IVT doses then stabilized between the second and third doses, suggesting little potential for intraocular accumulation of the drug. Serum concentrations of APL-2 peaked 6 days after each IVT injection then exhibited exponential declines with minimal concentrations being measured 28-days post-dose (immediately prior to the next IVT dose). Mean minimal serum APL-2 concentrations (26 to 28 days after IVT injection) were 15 to 30% of the corresponding maximal concentration.

Mean maximal serum concentrations of APL-2 after the tenth IVT dose were significantly lower (27 to 57%) than those achieved after the initial dose. Similarly, mean minimal serum concentrations of APL-2 (26-days after the tenth injection) were roughly 50% lower than those determined 28-days after the initial dose.

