8. STUDY PROCEDURES

8.1 Study Design

This is a Phase II, prospective, multicenter, randomized, single-masked, sham-controlled study to assess the safety, tolerability and evidence of activity of multiple IVT injections of APL-2 in subjects with GA associated with Age-Related Macular Degeneration.

Patients diagnosed with GA associated with age-related macular degeneration in the study eye and who meet all inclusion/exclusion criteria will be included in the study. The study will randomize approximately 240 subjects to obtain at least 200 evaluable subjects across 40 multinational sites.

Patients should be screened 14 (\pm 5) days before receiving APL-2. Upon entry into the study, patients will be assigned a subject screening number. Subjects who meet all inclusion and exclusion criteria and are confirmed as eligible by the CRC will return to the clinic for the randomization visit (Day 0) and randomized as outlined in [Section 7.1](#).

All subjects will return to the clinical site on Day 7 to assess acute safety after the first injection. After that, subjects in the monthly groups will return to the clinical site for additional APL-2 (or

[figure not shown]

Sham) injections and study procedures every month until Month 12. Subjects in the EOM groups will return to the clinical site for additional APL-2 (or Sham) injections and study procedures every two months until Month 12. All subjects will return for follow-up visits 3 and 6 months after Month 12 (Months 15 and 18, respectively)

Subjects who discontinue study treatment, can continue participation in the study and return to the clinical site for their scheduled study procedures (with the exception of APL-2/Sham administration).

Subjects who fully withdraw from the study before Month 12, should complete the Termination Visit.

See Study Outline below.

AM = APL-2 Monthly. SM = Sham Monthly. AEOM = APL-2 Every-Other-Month. SEOM = Sham Every-Other-Month. D = Day. M = Month.
 SMC = Safety Monitoring Committee. SMC will review cumulative safety data after the first 20 subjects have completed Day 7, Month 2 and Month 6 visits.
 * Eligibility to be confirmed by Central Reading Center.

Safety will be assessed throughout the study; serial blood samples and urine samples will be collected. Blood samples will also be collected for the PK assessment of APL-2.

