10.5.1 Withdrawal

Participants may choose to discontinue from treatment or to completely withdraw from this study for any reason at any time without penalty or prohibition from enrolling in other clinical protocols.

Participants wishing to withdraw from the study completely will be offered an early termination visit. This early termination visit will include the examinations outlined in [Section 8.3.6](#).

Participants wishing to discontinue treatment but willing to continue with other study procedures, will return to the clinical site for follow-up visits, as per protocol, every month or every two months until Month 12 and then Month 15, and a Termination Visit at Month 18.

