### **4.4. PHARMACOKINETIC ENDPOINTS**

Plasma APL-2 concentrations will be determined from multiple samples taken during the course of the study - screening, and at each visit from Day 7 to termination (Day 540).

$C_{max}$  should occur at Day 7 ( $C_{Day 7}$ ).

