### **5.7. PHARMACOKINETIC (PK) POPULATION**

The PK population will include all subjects in the safety population who have at least one quantifiable concentration of APL-2 (even if <LLOQ).

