### 6. GENERAL ASPECTS FOR STATISTICAL ANALYSIS

#### 6.1. GENERAL METHODS

All statistical tests will be 2-sided at the 0.1 level of significance. To understand the clinical significance of the estimated treatment effects and to aid interpretation of the formal hypothesis testing 2-sided 95% CI will also be provided. There will not be any adjustments for multiple comparisons.

For all independent ophthalmic assessments (performed by DARC laboratory), if assessments by only two independent readers are available, then the mean of the 2 readings will be used in the calculation of summary statistics. If assessments by three independent readers are available, then the median of the three readings will be used for the summary calculations.

Continuous variables will be summarized using the number of non-missing observations (n), mean, standard deviation (SD), median, minimum, and maximum. Geometric mean and coefficient of variation (CV) will be included for PK parameters, where appropriate. Categorical variables will be summarized using frequencies and percentages. Unless stated otherwise, for all percentages, the number of subjects in the analysis population for the treatment group will be the denominator.

Unless otherwise specified, the estimated mean and median for a set of values should be printed out to 1 more decimal place than the original values, and standard deviations should be printed out to 2 more decimal places than the original values. The minimum and maximum should report the same number of decimal places as the original values. Percentages will be displayed with 1 decimal place; except percentages will not be presented when the count is zero and 100% will be presented as an integer.

Unless stated otherwise, baseline will be taken as the last available non-missing assessment prior to first study drug administration.

Subjects can discontinue treatment but remain in the study for follow-up. All assessments will be included in summary tables or analyses unless stated otherwise.

For all summary tables, data will be presented by treatment group and by pooled sham and pooled APL-2. For summaries by-visit pooled sham and pooled APL-2 will only be presented for the bi-monthly visits. The treatment group labels for summary tables will be:

- APL-2 Monthly
- APL-2 EOM
- APL-2 Pooled
- Sham Monthly
- Sham EOM
- Sham Pooled

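### SAP 9.1 sets no dosing condition on its APL-2 trough summaries, so samples from subjects who stopped or missed injections enter the Month 1 to 12 rows and can pull them down

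*SAP*

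**What the plan says.** - **What is summarised.** SAP 9.1: "APL-2 trough concentrations will be summarized by treatment group at each protocol specified time point using descriptive statistics including the interquartile range". The median profile plots use the same concentrations. Neither is limited by time since last dose or by treatment status.
- **Who is included.** The PK population (SAP 5.7) takes safety-population subjects "who have at least one quantifiable concentration of APL-2 (even if <LLOQ"). This rule selects subjects. It removes no individual sample.
- **Default for off-treatment data.** SAP 6.1 notes that subjects can stop treatment and stay in follow-up, then says: "All assessments will be included in summary tables or analyses unless stated otherwise". Section 9 makes no exception.
- **Off-treatment attendance.** Protocol 8.1: "Subjects who discontinue study treatment, can continue participation in the study and return to the clinical site for their scheduled study procedures". Protocol 10.5.1 repeats this.
- **Sampling times.** SAP 4.4: "screening, and at each visit from Day 7 to termination (Day 540").
- **Values below quantification (BLQ).** Under SAP 6.2.2 they count as zero in descriptive statistics, or as the LLOQ for the geometric mean. A BLQ value between two quantifiable ones is set to the LLOQ unless its exclusion can be justified.
- **Labels.** SAP Section 13, item 4, describes all the samples as troughs, yet the same item, with SAP 4.4 and 9.2, takes Day 7 as the maximum concentration.

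**The concern.** A trough is the concentration at the end of a dosing interval. A sample taken at a Month 8 visit from a subject last injected at Month 4 is not a trough, yet under these rules it counts in that arm's Month 8 trough row, possibly as zero. As more attending subjects come off treatment, the row can fall although exposure in those still being injected is unchanged.

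Two things give this some weight. First, SAP Section 13 drops AUC, Tmax and half-life, so these tables and plots, with Day 7 among them, are essentially the whole PK result. Second, a real fall in exposure with repeated dosing is an open question. Protocol 4.1.3.1 reports for monkeys: "Mean maximal serum concentrations of APL-2 after the tenth IVT dose were significantly lower (27 to 57%) than those achieved after the initial dose". It adds that minimal concentrations after the tenth injection were roughly 50% lower than after the first. An arm-level row that mixes injected and uninjected subjects cannot by itself tell such a fall from discontinuation.

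A separate, smaller matter is labelling. Day 7, Month 15 and Month 18 samples carry the trough label at their own time points.

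**Working it through.** **1. Sampling schedule.** Counting draws in the flow charts:
- Monthly: screening, Day 7, Months 1 to 12, Months 15 and 18 = 1 + 1 + 12 + 2 = 16.
- Every other month (EOM): screening, Day 7, Months 2, 4, 6, 8, 10 and 12, Months 15 and 18 = 1 + 1 + 6 + 2 = 10.

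This reproduces the 10/16 in Protocol 9.9, although the note there gives the order as M/EOM, the reverse of the counts. Samples that fall one dosing interval after a scheduled injection number 12 of 16 and 6 of 10.

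**2. Decay model.** Remaining fraction after t days = 2^(−t/T), with T = 10.4 days, the apparent monkey serum half-life after intravitreal injection (Protocol 4.1.3.1). No human value is given, so T is varied from 7 to 14 days. As a check, from the Day 6 serum peak to Days 26 and 28 the model gives 2^(−20/10.4) = 26% and 2^(−22/10.4) = 23%. The protocol states 15 to 30% for monkeys.

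**3. What a missed injection leaves, relative to the usual trough.**

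| Situation | Extra days | T = 10.4 | T = 7 to 14 |
|---|---|---|---|
| One missed monthly | 30 | 14% | 5 to 23% |
| Two missed monthly | 60 | 2% | 0.3 to 5% |
| One missed EOM | 60 | 2% | 0.3 to 5% |

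Allowing also for the 3.2-day vitreous half-life, with monthly dosing at steady state, gives 13.7% and 1.9% for one and two missed injections, so the simple model is adequate.

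**4. Effect on the arm summary.** Let f be the fraction of sampled subjects off treatment and r their residual ratio.
- Mean ratio = 1 − f(1 − r).
- With off-treatment values near zero, the overall median sits at the (0.5 − f)/(1 − f) quantile of the on-treatment distribution, taken as lognormal with σ = √ln(1 + CV²).

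The documents give neither f nor the CV; both are assumed.

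| f | Fall in mean, r = 0 | Fall in mean, r = 0.135 | Fall in median, CV 50% | Fall in median, CV 30 to 80% |
|---|---|---|---|---|
| 5% | 5% | 4% | 3% | 2 to 4% |
| 10% | 10% | 9% | 6% | 4 to 9% |
| 20% | 20% | 17% | 14% | 9 to 20% |

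If f rose from 0 to 20% by Month 12, the mean would drift down by about 20% with on-treatment exposure constant. Matching the full monkey trough fall of roughly 50% would need f near 50% (1 − 0.5 = 0.5), so discontinuation in the assumed range could imitate or enlarge a moderate fall but not produce all of a large one.

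**5. Samples outside the dosing interval.** A Day 7 value is about 2^(23/10.4) = 4.6 times a Day 30 trough (3.1 to 9.8 over the half-life range). Month 15 is 90 days after the Month 12 injection: 2^(−60/10.4) = 2% of a monthly trough and 2^(−30/10.4) = 14% of an EOM trough. The table is by visit, so none of these values enters a Month 1 to 12 row.

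**The case against.** The strongest reply is that the reporting package already shows the reader what is happening. SAP 9.1 tabulates BLQ counts, gives individual profiles at actual sampling times and plots medians. SAP 6.1 puts time since last dose in the relevant listings. SAP 7.1 reports, by visit and arm, how many subjects were injected and how many had stopped. SAP 7.6 summarises missed injections. SAP 5.10 requires a documented data review before lock. There is no PK hypothesis test, and Protocol 11.6 rests the Phase III decision on the one-year follow-up analysis.

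Most of this stands, and it is why the point is minor. It does not remove the point: none of these displays changes what enters the trough row, and the median moves less than the mean but still moves.

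A reader might also infer more than the documents support:
- **That the troughs are biased low and will fall.** This depends on f, which is not given. The 15 to 20% in Protocol 11.3.4 is loss to follow-up, and those subjects give no later samples. Subjects who stop injections may later leave altogether, and single missed injections need not produce a trend.
- **That Day 7, Month 15 and Month 18 samples contaminate the troughs.** They affect only their own rows. A Day 7 value read as a trough errs high, and the fall at Months 15 and 18 is true washout.
- **That off-treatment values are usually zero.** After one missed monthly injection about 14% of the trough may remain, which may be quantifiable. A BLQ value followed by renewed dosing may be set to the LLOQ. Zero is the likelier treatment after permanent discontinuation, where no quantifiable value follows.

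**Conclusion.** The concern holds in a limited form. As written, SAP 6.1 and 9.1 together place off-treatment samples in the Month 1 to 12 trough rows, so the arm summaries can be biased low and can drift down without any change in on-treatment exposure. The size rests on three things that the documents do not supply: a human half-life (monkey 10.4 days used), the off-treatment fraction among sampled subjects, and the between-subject CV. Over the assumed range of 5 to 20% off treatment, the distortion is about 5 to 20% in the mean and about 3 to 14% in the median at a CV of 50%.

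A larger distortion in the geometric mean is a tempting inference, but it would need an assumed ratio of trough to LLOQ, and SAP 9.1 does not name that statistic for concentrations. Nor do the documents show that discontinuation differs between the monthly and EOM arms. Severity is minor: the summaries are descriptive and no endpoint test depends on them.

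**What to change.** In SAP 9.1:
- Limit the trough table and median trough plots to pre-injection samples for which the immediately preceding scheduled injection was given. Say explicitly that they are pre-injection: Protocol 8.3.4 lists the PK draw before the injection but does not state this.
- Define eligibility by time since last dose, with a stated window. Two successive ±6-day visits can differ from the nominal interval by up to 12 days, but 30 ± 12 days admits samples at 18 to 42 days, about a five-fold spread at a 10.4-day half-life (2^(24/10.4) = 4.9), so a narrower window deserves thought. The first trough in each schedule (Month 1 monthly, Month 2 EOM) can vary by only ±6 days, because Day 0 has no window.
- Report Day 7 as C_Day7. Show Month 15, Month 18 and off-treatment samples separately, by time since last injection.
- Keep every sample in the listings and, optionally, an all-samples table as supportive.

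The cost is SAP wording and one flag built from a time-since-last-dose variable already planned for the listings. The downside is a smaller n at later visits and a selected on-treatment subset that can change from visit to visit, so the table should show n and say so. SAP 4.1 and 8.1.3 record that the 12-month results had already been reviewed, so any re-run Month 12 table should be labelled as added after that review.
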